## **1.6 Dose Rationale and Risk/Benefits**

### **Summary of known and potential risks and benefits, if any, to subjects:**

Metformin's most serious toxicity is lactic acidosis, occurring in three of 100,000 patient-years of use. Risk is significantly reduced when metformin use is avoided in those patients with hepatic, cardiac, or renal compromise. However,

metformin's risk of lactic acidosis may be overstated since the recent evaluation of metformin associated lactic acidosis cases from 347 trials showed that the risk of lactic acidosis with metformin was not significantly increased compared with other antiglycemic agents. Minor gastrointestinal upset is the most common toxicity, leading to cessation of therapy in less than 5% of individuals. Metformin does not induce hypoglycemia. The possible societal benefits are large since this will allow us to learn about the pharmacodynamic effects of metformin in normal tissue protection during radiation.

**Description and justification for the route of administration, dosing regimen and treatment period:**

Metformin will be administered orally since this is the route of administration currently approved by the FDA. Beginning one-two weeks prior to planned external beam radiation therapy, the drug will be initiated at a dose of 500mg orally daily for 3 days and will then be increased to 500 mg twice daily. If tolerated, metformin will be further increased to 1000mg twice daily after day 6. Subjects will maintain 1000 mg twice a day dosing until two weeks post radiation.

There are currently multiple studies on-going using doses from between 500 mg twice daily up to 2500 mg per day in the treatment arms. There are also studies using the extended release form for a dose of 1500 mg daily. We have chosen our starting dose and escalation regimen to minimize side effects. The chosen standing dose is based on metformin's therapeutic range (minimal therapeutic dose in diabetic patients is 1500-2000 mg a day). The time of planned exposure to metformin will be 8-10 weeks. We will allow a window of an additional 2 weeks in the event that there are delays in the treatment scheduling but no patients will receive metformin for more than 12 weeks.

**Rules for dose modification: Toxicity monitoring, dose modification and treatment of complications:**

Particular attention will be paid in the first three days of treatment. Patients will take 500mg/day for 3 days. From day 4, 500mg twice daily and then in 3 days (Day 6) dose escalation to 1000mg twice daily will be achieved. A phone call on the day of each dose escalation will be made in order to evaluate the tolerability of the drug and also weekly thereafter. Patients will be instructed to contact the clinical investigators should any side effects occur during the study.

In the event that an Iodinated IV contrast dye load for CT scanning is required at some point during the metformin treatment period, the drug will be held 48 hours in advance of administration of IV dye, as is the standard practice among patients taking metformin. This measure is generally considered to be conservative as the risk of lactic acidosis in patients taking metformin has not been shown to be higher than that of the general population after IV contrast dye in recent literature. Nevertheless, this measure is in compliance with current

American College of Radiology guidelines. Metformin will be resumed at the last dose the subject was receiving prior to being held and if escalation was planned as previously described.

Toxicity will be evaluated using the most recent version (version 4) of the NCI toxicity criteria, i.e. the NCI Common Terminology Criteria for Adverse Events (CTCAE) version 4.0. The CTCAE provides descriptive terminology and a grading scale for each adverse event listed. A copy of the CTCAE can be found at <http://ctep.cancer.gov>.

Grade 1 toxicity: Patient will be maintained on full dose.

Grade 2 toxicity: Dose will be reduced by 50% until grade 1 or lower. If symptoms are not resolved the treatment will be discontinued definitively.

Grade 3 toxicity (probably or definitely drug related): Treatment will be interrupted and reassessment of toxicity will be performed daily. If toxicity is reduced to grade 1 or lower dose will be reduced by 50%. If toxicity is not resolved after 3 days the treatment will be discontinued definitively.

Grade 4 toxicity (probably or definitely drug related): Treatment will be discontinued definitively.

In case of grade 1 or 2 diarrhea (the most frequent side effect), concomitant loperamide will be provided and with grade 2 diarrhea the dose will be reduced by 50% until grade 1 or lower.

### **Risk benefit analysis**

The risks using metformin are small in this protocol with strict inclusion and exclusion criteria. It is unknown if metformin improves outcomes in HNSCC and this study is not designed to evaluate efficacy of metformin in HNSCC, but this study is designed to evaluate whether the sequelae of treatment from external beam radiation are mitigated by use of metformin. Hence, the potential direct benefits to subjects in this study include the possibility of decreased, xerostomia, dysphagia, fatigue and other sequelae of RAI. Further, the possible societal benefits are large since this will allow us to learn about the pharmacodynamic effects of metformin in radiation treatment, tolerability and safety profile.

Metformin is a widely used drug with an extensive safety record. In order to further minimize the risk of toxicity, strict exclusion criteria will be applied. This trial could lead to a better understanding of the properties of the cancer microenvironment. The hypothetical risk of loss of confidentiality is minimized by the layers of security in place as detailed above.

### **Potential risks:**

There is a potential risk of development of side effects related to metformin administration. Most commonly reported side effects in 1-5% of patients are

nausea, vomiting, and abdominal pain. An extremely low risk of lactic acidosis is present (0.001%) which is minimized by excluding patients with renal dysfunction, hepatic dysfunction, cardiac impairment, pulmonary impairment, or excessive alcohol use. There is also a risk of loss of confidentiality which will be minimized as outlined in section 0.

### **Potential benefits:**

Metformin may provide a radioprotective effect and mitigate the sequelae of external beam radiation. Furthermore, metformin may alter tumor metabolism and improve outcomes in various cancers. This study is designed to evaluate whether the sequelae of radiation are mitigated by metformin and thus some patients may benefit from this study by taking metformin. With regards to cancer benefit, this study is not designed to evaluate efficacy in cancer treatment and it is unknown if metformin improves outcomes in cancer.

## **2.0 STUDY OBJECTIVES**

1. To assess the capacity of metformin to alter the cytokine and exosome profiles.
2. To assess the capacity of metformin to mitigate known side effects of external beam radiation therapy including inflammation, mucositis, dysphagia, xerostomia, and fatigue.

### **2.1 Primary Objective:**

We have chosen a cytokine/chemokine profile analysis as a surrogate marker of trending inflammatory reaction. This response drives the severity of mucositis/xerostomia and acute radiation toxicity. The blood and saliva counts will be compared in the pre-treatment sample, during treatment samples and post treatment samples. Luminex technology with 40 cytokines markers will be used (Luminex technology with the Milliplex MAP Human Cytokine/chemokine Magnetic kit I (41 analytes) (sCD40L, EGF, Eotaxin, FGF-2, Flt-3 ligand, Fractalkine, G-CSF, GM-CSF, GRO, IFN- $\alpha$ 2, IFN- $\gamma$ , IL-1 $\alpha$ , IL-1 $\beta$ , IL-1ra, IL-2, IL-3, IL-4, IL-5, IL-6, IL-7, IL-8, IL-9, IL-10, IL-12 (p40), IL-12 (p70), IL-13, IL-15, IL-17A, IP-10, MCP-1, MCP-3, MDC (CCL22), MIP-1 $\alpha$ , MIP-1 $\beta$ , PDGF-AA, PDGF-AB/BB, RANTES, TGF- $\alpha$ , TNF- $\alpha$ , TNF- $\beta$ , VEGF). Blood and saliva samples will be drawn before, during and immediately after treatment and every three months thereafter for one year. All blood samples will be taken by a phlebotomist who will be blinded as to whether the patient is in the experimental (radiation + metformin) or control (radiation + placebo) groups.

### **2.2 Secondary Objective:**

- Assess safety and tolerability of metformin treatment in subjects undergoing external beam radiation treatment for head and neck cancer.

- To determine the effect of metformin treatment on symptoms of **xerostomia** as assessed by the Xerostomia Questionnaire (XQ)
- To determine the effect of metformin treatment on symptoms of **mucositis** as assessed by WHO classification
- To determine the effect of metformin treatment on symptoms of **dysphagia** as assessed by the MD Anderson Dysphagia Inventory
- To determine the effect of metformin treatment on symptoms of **Fatigue** as assessed by the Multidimensional fatigue inventory (MFI).

### 2.3 Primary Study Endpoints

- a) Cytokine/chemokine profile
- b) Exosome profile.

### 2.4 Secondary Study Endpoints

Measures of

- a) Mucositis
- b) Dysphagia
- c) Xerostomia
- d) Fatigue.

### 2.5 Primary Safety Endpoints

Toxicity will be evaluated using the most recent version (version 3) of the NCI toxicity criteria, i.e. the NCI Common Terminology Criteria for Adverse Events (CTCAE) version 4.0. The CTCAE provides descriptive terminology and a grading scale for each adverse event listed. A copy of the CTCAE can be found at <http://ctep.cancer.gov>. *Any grade 3 or 4 SAE will require immediate notification to the DSMB and IRB. Metformin will be held for any grade 3 or 4 SAE.*

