### 1.2 Background and Rationale:

#### Effects of Radiation on Normal Tissue and Systemic Effects

Treatment for Head and Neck Cancer has used radiation as one of the foundational components to achieve expected cure rates. Protocols have been well established to maximize tumor kill rate and minimize collateral damage to surrounding tissue, yet the effects of radiation on normal tissue remains profound in the head and neck region. Oral mucositis, swallowing, xerostomia and fatigue are the main drivers that affect quality of life status post treatment.

Oral mucositis is a common, problematic, and painful complication of cancer therapy, in the regimens that include radiation therapy for the head and neck cancer. Oral mucositis is a treatment-induced morbidity that has substantial impact on day-to-day functioning. In addition to the common need for, and inadequate pain control with, narcotics, the profound clinical impact of oral mucositis also includes weight loss, difficulty eating and swallowing, dehydration, need for nutritional support, and reduced performance status, as well as secondary infections and diminished quality of life (QOL).

A majority of patients receiving combined chemoradiotherapy for head and neck cancer (HNC) can be expected to develop severe (WHO Grade 3-4) oral mucositis and nearly all HNC patients receiving RT with concurrent cisplatin are expected to develop oral mucositis (WHO Grade 2 or higher). Standard chemoradiotherapy for locally advanced head and neck (HNC), whether in the post-operative or definitive setting, currently consists of intensity-modulated radiation therapy (IMRT) plus/minus systemic therapy. The monoclonal antibody cetuximab has also been shown to increase the efficacy of radiotherapy for locally advanced head and neck cancer, and the combination of IMRT plus either single-agent cisplatin or single-agent cetuximab is currently being tested head-to-head for patients with human papilloma virus (HPV)-related oropharyngeal cancer in the ongoing RTOG 1016 trial. In addition, two recently published Phase 3 studies of palifermin in patients receiving RT plus single-agent cisplatin for HNC reported an overall incidence of severe (WHO Grade 3-4) oral mucositis among placebo patients of 67% in one study and 69% in the other. Oral mucositis prevention and management remains a substantial unmet need.

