## **6.2 Definition of Dose-Limiting Toxicities and early stopping rules:**

Toxicity will be evaluated using the most recent version (version 4) of the NCI toxicity criteria, i.e. the NCI Common Terminology Criteria for Adverse Events (CTCAE) version 4.0. The CTCAE provides descriptive terminology and a grading scale for each adverse event listed. A copy of the CTCAE can be found at <http://ctep.cancer.gov>.

Grade 4 toxicity (probably or definitely drug related): Treatment will be permanently discontinued.

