## **6.3 Dose Delays and Dose Modifications**

Toxicity will be evaluated using the most recent version (version 4) of the NCI toxicity criteria, i.e. the NCI Common Terminology Criteria for Adverse Events (CTCAE) version 4.0. The CTCAE provides descriptive terminology and a grading scale for each adverse event listed. A copy of the CTCAE can be found at <http://ctep.cancer.gov>.

Grade 1 toxicity: Patient will be maintained on full dose.

Grade 2 toxicity: Dose will be reduced by 50% until grade 1 or lower. If symptoms are not resolved within 3 days of toxicity development the treatment will be interrupted definitively.

Grade 3 toxicity (probably or definitely drug related): Treatment will be interrupted. Toxicity will be evaluated daily and if toxicity improves to grade 1 or lower dose will be reduced by 50%. If toxicity is not improved or resolved or reduced to grade 1, treatment will be interrupted definitively.

Grade 4 toxicity (probably or definitely drug related): Treatment will be permanently discontinued.

In case of grade 1 or 2 diarrhea (the most frequent side effect) a concomitant administration of loperamide will be provided.

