#### ***Serious Adverse Event***

Adverse events are classified as serious or non-serious.

A ***serious adverse event*** is any AE that is:

- fatal
- life-threatening
- requires or prolongs hospital stay
- results in persistent or significant disability or incapacity
- a congenital anomaly or birth defect
- an important medical event

Important medical events are those that may not be immediately life threatening, but are clearly of major clinical significance. They may jeopardize the subject, and may require intervention to prevent one of the other serious outcomes noted above. For example, drug overdose or abuse, a seizure that did not result in in-patient hospitalization, or intensive treatment of bronchospasm in an emergency department would typically be considered serious.

All adverse events that do not meet any of the criteria for serious should be regarded as ***non-serious adverse events***.

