## **8.4 Stopping Rules:**

Grade 4 toxicity (probably or definitely drug related): Treatment will be discontinued definitively.

Participants will be discontinued from study drug as per physician discretion

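### Section 2.5 holds metformin for any grade 3 or 4 SAE whatever its cause, while the other dosing sections require action at those grades only for drug-related toxicity, and nothing says how the rules combine

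*Combined protocol and SAP*

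**What the plan says.** Section 2.5 (Primary Safety Endpoints) attaches two consequences to a serious adverse event of grade 3 or 4. For reporting: "Any grade 3 or 4 SAE will require immediate notification to the DSMB and IRB". For dosing: "Metformin will be held for any grade 3 or 4 SAE". Neither depends on cause. The section does not say when metformin may restart, or whether any event ends treatment for good.

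Section 6.3 works from toxicity grade and attribution. At grade 3: "Grade 3 toxicity (probably or definitely drug related): Treatment will be interrupted". At grade 4, with the same attribution condition, the stop is permanent. Sections 1.6 and 5.3 apply the same condition at both grades. Section 6.2 has a grade 4 rule only: "Grade 4 toxicity (probably or definitely drug related): Treatment will be permanently discontinued". Section 8.4 repeats it, "Grade 4 toxicity (probably or definitely drug related): Treatment will be discontinued definitively", and adds a general clause: "Participants will be discontinued from study drug as per physician discretion".

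Section 8.1 defines an SAE by seriousness, separately from grade and from cause. One criterion is that the event "requires or prolongs hospital stay".

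**The concern.** Two investigators who follow the protocol faithfully could treat the same patient differently. One reads 2.5 and holds the drug because the event is serious and of grade 3 or 4. The other reads 6.3, judges the event to be due to radiation, and finds no instruction to interrupt.

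The situation is foreseeable. Section 1.2 cites two trials of radiation plus single-agent cisplatin that "reported an overall incidence of severe (WHO Grade 3-4) oral mucositis among placebo patients of 67% in one study and 69% in the other", and a hospital admission is enough to make such an event an SAE. Mucositis is also a secondary endpoint, so under 2.5 a toxicity that metformin is hoped to reduce can itself interrupt metformin.

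What is at stake is patient safety, since a mandatory hold may or may not be applied, and drug exposure up to Visit 3. Dosing is planned until two weeks after radiation (5.2), which is when the Visit 3 samples are taken (6.1). The judgement that separates the rules is attribution, and under 5.9 the investigator and the assessing care providers know the arm when they make it.

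**Working it through.** No figure in the plan is at stake, so the check sets the dosing rules side by side. Here, related means judged at least probably related to the drug.

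| Section | Trigger | Must be related? | Grade 3 | Grade 4 | Resumption after a grade 3 event |
|---|---|---|---|---|---|
| 2.5 | SAE | No | Hold | Hold | Not stated |
| 1.6 | Toxicity | Yes | Interrupt | Permanent stop | Half dose at grade 1 or lower; permanent stop if unresolved after 3 days |
| 5.3 | Toxicity | Yes | Interrupt | Permanent stop | Half dose at grade 2; nothing stated if there is no improvement |
| 6.2 | Toxicity | Yes | No rule | Permanent stop | Not applicable |
| 6.3 | Toxicity | Yes | Interrupt | Permanent stop | Half dose at grade 1 or lower; otherwise permanent stop, no time limit given |
| 8.4 | Toxicity | Yes | No rule | Permanent stop, plus physician discretion | Not applicable |

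Applying the table to each kind of event:

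1. **Grade 3 or 4 SAE, not judged related.** Section 2.5 requires a hold with no restart rule. The other five sections mandate no action at that grade; 8.4 leaves it to the physician. This class includes events rated only possibly related, a category that the 8.5.1 reporting table groups with probable and definite but that the dosing rules leave out.
2. **Grade 4 SAE, related.** Section 2.5 says hold. Sections 1.6, 5.3, 6.2, 6.3 and 8.4 say permanent stop.
3. **Grade 3 SAE, related.** Sections 2.5, 1.6, 5.3 and 6.3 agree on interrupting. Section 2.5 is silent on resumption, and the other three disagree on it: grade 1 or lower in 1.6 and 6.3, grade 2 in 5.3.
4. **Grade 3 or 4 toxicity, related but not serious.** This lies outside 2.5, so the toxicity rules apply without conflict. It shows that the triggers differ as well as the attribution condition.

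The last step is to look for a rule of precedence. The only candidate is the note under the 8.5.1 table, which favours more stringent protocol requirements. It concerns the reporting of events. It can settle the difference between the immediate notification in 2.5 and the timelines in 8.5.1, but it does not reach dosing. No other section ranks or links the dosing rules.

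**The case against.** The best defence is that all the sections can be followed at once. A hold is an immediate step and a permanent stop is a final disposition. One could hold for any grade 3 or 4 SAE, then stop for good if it is grade 4 and related. Section 2.5 never says that drug resumes after grade 4, and 6.3 never says that drug continues through an unrelated SAE. This reading is coherent and softens the grade 4 difference considerably. But no section states it, and it still leaves an unrelated SAE with a hold and no way back onto drug.

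Three stronger readings are tempting and should not be drawn.

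- **That an unrelated event triggers nothing outside 2.5.** Section 8.4 allows discontinuation at physician discretion, and 4.5.1 lists safety reasons as judged by the investigator. The grade 2 rule in 6.3 carries no attribution condition: the dose is halved, and treatment ends if symptoms have not resolved within 3 days. The accurate statement is that no action is mandated at grade 3 or 4.
- **That placebo patients are exempt from the hold.** Section 2.5 names only metformin, but the protocol often uses that word for study drug in general, for example in the compliance and visit sections, and 6.3 and 8.4 speak of treatment. The wording needs correcting; it does not show an intended difference between arms.
- **That the conflict changes what the primary analysis compares.** Section 7.1 compares by randomisation assignment and 7.3 includes all randomised participants with any data. A hold alters exposure. It neither removes patients nor redefines the comparison.

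**Conclusion.** The inconsistency is real and should be corrected. It rests on the text alone: 2.5 is triggered by seriousness and grade regardless of cause, the other sections by grade and attribution, and no section says how the two combine. The divergence is clearest for a grade 3 or 4 SAE not judged related. For a related grade 4 SAE it is milder, because hold and stop can be read as successive steps.

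The number of patients affected cannot be derived from the documents. A reader might multiply the cited mucositis rates by an assumed share of cases that are serious and not attributed to the drug. With 25 patients in the metformin arm, a 10% share gives 25 × 0.67 × 0.10 = 1.7 patients and a 50% share gives 25 × 0.69 × 0.50 = 8.6. The documents do not support such a count, for three reasons:

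- The share is unanchored, and it drives the result.
- The 67% and 69% are WHO-grade rates under cisplatin chemoradiation. This trial grades toxicity by CTCAE and requires no chemotherapy for entry (4.1).
- Many patients with severe mucositis may first pass through grade 2. Read literally, the unconditional grade 2 rule could already have reduced or ended their dosing, so it is not established that they would otherwise have continued on drug.

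The consequence is limited to safety handling and drug exposure. The power statements and the planned comparison by arm do not change.

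**What to change.** Reconcile 2.5 with 1.6, 5.3, 6.2, 6.3 and 8.4 in one dose-modification table that applies to study drug in both arms, and have every section refer to it. For each grade the table should state:

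- whether the trigger is an SAE, a toxicity, or either;
- whether attribution to the drug is required, and at what level;
- whether the action is a hold or a permanent stop, and how one leads to the other;
- whether and when drug resumes, which also settles the differing grade 3 resumption thresholds in 1.6, 5.3 and 6.3.

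The clinical team decides which rule stands; this review takes no position on that. The cost is a wording amendment submitted to the IRB, with no change to sample size, randomisation or planned analyses.

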## 3.0 STUDY DESIGN

**Purpose of the study:** To assess the radioprotective effect of metformin in subjects with head and neck cancer by evaluating both the ability of metformin to mitigate known side effects of radiation therapy as well as alter the exosome profile in the serum.

